11.9.2 Tumor Lysis Syndrome Laboratory Monitoring

Tumor lysis syndrome prophylaxis must be initiated prior to all lead-in dosing of AMG 176 and prior to all subsequent dose escalations (ie, first dose on the targeted cohort dose level). Subjects must be hospitalized and monitored the night before AMG 176 administration and will continue until at least 24 hours post-dose. Chemistry labs must include serum potassium, phosphorous, calcium, uric acid, and creatinine, and be performed for the following timepoints:

- AMG 176: pre-dose (within 4 hours before AMG 176 administration), 2, 4, 8, 12, and 24 hours after the start of AMG 176 infusion. Note: For AMG 176 180 mg/m² with lead-in dose: Subjects will also be hospitalized in week 2.
- Azacitidine: pre-dose, 6 to 8 hours after each new dose during ramp-up and 24 hours after reaching final dose

Since subjects on this trial may be at risk for developing TLS, measures will be implemented to help reduce and manage this risk, including staggered initiation of the two BH3 mimetics, ramp up dosing, and hospital admission during cycle 1 during the first doses of AMG 176 and azacitidine.

^a not directly or probably attributable to therapeutic agent

 $^{^{\}rm b}$ if no institutional ULN is specified, age/sex ULN creatinine may be defined as follows: > 1 to < 12 years of age, both male and female, 61.6 μmol/L; \geq 12 to < 16 years, both male and female, 88 μmol/L; \geq 16 years, female 105.6 μmol/L, male 114.4 μmol/L.

Protocol Number: 20200392

Date: 28 April 2022 Page 134 of 149

To further mitigate any possible risk of TLS, several measures will be implemented:

Electrolyte levels, including serum potassium, calcium, phosphorous, and uric acid
will be checked prior to treatment to make sure they are within the normal range.
Hyperkalemia (Potassium > 5.0) should be corrected prior to starting therapy.
Phosphate binders should be started (unless contraindicated) in subjects with
elevated phosphorous.

- Subjects with medium (white blood cell [WBC] 10 to 20) risk for tumor lysis should be initiated on allopurinol (or other uric acid lowering treatment) prior to therapy.
 Subjects with n > 20 should have cytoreduction (with hydrea) or delay therapy to make sure the WBC to less than 20 prior to starting therapy in protocol. If the uric acid is elevated above 9, the patient should be given a dose of rasburicase per institutional protocol.
- Oral and when needed, IV hydration, will also be implemented per institutional standards to help mitigate the risk for TLS.

11.9.3 Prophylaxis and Management of Tumor Lysis Prophylaxis

The management recommendations below focus on the minimum initial responses required. If a diagnosis of TLS is established, ongoing intensive monitoring and multi-disciplinary management will be conducted per institutional protocols (Coiffier et al, 2008; Cairo et al, 2004).

Tumor lysis syndrome prophylaxis includes:

- Allopurinol or equivalent should be used to reduce uric acid level per SOC. This
 should be initiated at least 72 hours prior to dosing. Treatment may need to be
 continued for up to 5 weeks. Other agents to reduce uric acid level, such as
 rasburicase, may be used per principal investigator discretion and the institutional
 guidelines. Dosing per institutional guidelines.
- All patients should have WBC count less than 25 x 10⁹/L prior to initiation of azacitidine. Cytoreduction prior to treatment may be required.
- Hospitalization and monitoring: beginning the night before AMG 176 administration until at least 24 hours post-first AMG 176 dose.
- Intravenous hydration must be started the night before AMG 176 administration and to be continued until at least 24 hours post—dose during hospitalization as clinically tolerated (see below for more details about the level of IV hydration required)
- Monitoring of electrolyte values is required prior to dosing anytime a dose is higher than one previously given to the subject. This will include at the following times for:

AMG 176:

- Prior to the week 1. day 1 dose
- Prior to each dose during the lead-in period
- Prior to the initial dosing at the target dose level

Azacitidine:

- Pre-dose, 6 to 8 hours after each new dose during ramp-up, and 24 hours after reaching final dose
- Prior to administering these doses, all electrolyte values (including lactate dehydrogenase [LDH], potassium, uric acid, phosphorus, calcium, and creatinine) must be reviewed and within normal range (samples must be drawn within 24 hours

Protocol Number: 20200392

Date: 28 April 2022 Page 135 of 149

prior to dosing of AMG 176). The investigator's decision to proceed with AMG 176 treatment initiation will be based on these laboratory values.

- Within the first 24 hours after either the first dose or dose escalation, if any laboratory criteria for TLS are met, no additional AMG 176 doses should be administered until resolution. A rapidly rising serum potassium is a medical emergency.
- Prophylactic dose reductions for potassium, phosphorus and/or uric acid values at the high end of normal range should be considered.
- If the potassium, uric acid, inorganic phosphate and/or creatinine values are higher than the normal range or the calcium is lower or higher than the normal range, this (these) value(s) can be approved following a discussion between the Amgen medical monitor and investigator.
- On the AMG 176 dosing days chemistry labs must be performed pre-dose (within 4 hours before AMG 176 administration), 2, 4, 8, 12, and 24 hours after the start of AMG 176 infusion. Pre-dose labs will be used as baseline to assess potential electrolytes abnormalities occurring post AMG 176 administration. These labs must be reviewed in real time by the investigator.
- All 24-hour laboratory assessments may be taken ± 2 hours, if necessary.
- Perform hematology labs at pre-dose (within 4 hours before AMG 176 administration) and 24 hours after the start of AMG 176 infusion.
- Monitor for signs and symptoms of TLS (eg, fever, chills, tachycardia, nausea, vomiting, diarrhea, diaphoresis, hypotension, muscle aches, weakness, paresthesias, mental status changes, confusion, and seizures). If any clinical features are observed, recheck potassium, phosphorus, uric acid, calcium and creatinine within 1 hour.
- Nephrology (or acute dialysis service) consultation should be considered on admission (based on investigator discretion) for hospitalized subjects per institutional guidelines to ensure emergency dialysis is available and the appropriate staff is aware and prepared.

All subjects will receive TLS prophylaxis as described above. Allopurinol or equivalent should be used to reduce uric acid level. This should be initiated at least 72 hours prior to dosing. Treatment may need to be continued for up to 5 weeks. Other agents to reduce uric acid level, such as rasburicase, may be used per investigator discretion and institutional guidelines.

Within the first 24 hours after either the first dose or dose escalation, if any laboratory criteria below are met, no additional AMG 176 doses or azacitidine should be administered until resolution. A rapidly rising serum potassium is a medical emergency.

Nephrology (or other acute dialysis service) should be contacted/consulted (per institutional guidelines to ensure emergency dialysis is available) on admission for any subject hospitalized prophylactically or in response to laboratory changes.

Intravenous (IV) fluids (eg, D5 1/2 normal saline) should be initiated at a rate of at least 1 mL/kg/hr rounded to the nearest 10 mL (target 150 to 200 mL/hr; not < 50 mL/hr).

Protocol Number: 20200392

Date: 28 April 2022 Page 136 of 149

Modification of fluid rate should also be considered for individuals with specific medical needs.

Monitor for symptoms or signs of TLS (eg, fever, chills, tachycardia, nausea, vomiting, diarrhea, diaphoresis, hypotension, muscle aches, weakness, paresthesias, mental status changes, confusion, and seizures). If any clinical features are observed, recheck potassium, phosphorus, uric acid, calcium, and creatinine within 1 hour and perform ECG.

Vital signs should be taken at time of all blood draws or any intervention.

For subjects with risk factors for TLS (eg, circulating blasts, high burden of leukemia involvement in bone marrow, elevated pre-treatment LDH levels, or reduced renal function), consider additional measures, including increased laboratory monitoring and reducing azacitidine starting dose.

The management recommendations below focus on the minimum initial responses required (Roberts et al, 2016). If a diagnosis of TLS is established, ongoing intensive monitoring and multi-disciplinary management will be per institutional protocols.

Protocol Number: 20200392

Date: 28 April 2022 Page 137 of 149

Table 11-6. Tumor Lysis Syndrome Management Recommendations

Abnormality Management Recommendations Hyperkalemia (including rapidly rising potassium) • Potassium ≥ 0.5 mmol/L • Recheck potassium, phosphorus, uric acid, calcium and creatinine in 1-hour STAT. If further ≥ 0.2 mmol/L increase from prior value (even if potassium within increase in potassium, but still < upper limit of normal normal limits [WNL]) (ULN), manage as per potassium ≥ ULN. Otherwise recheck in 1 hour. • Resume per protocol testing if change in potassium is < 0.2 mmol/L, and potassium < ULN, and no other evidence of tumor lysis. • At discretion of Investigator, may recheck prior to hospitalization. If stable or decreased, and still WNL, hospitalization is at discretion of the Investigator. Potassium phosphorus, uric acid, calcium and creatinine must be rechecked within 24 hours. • Potassium > upper limit of Perform STAT ECG and commence telemetry. normal Nephrology notification with consideration of initiating dialysis. Administer Kayexalate 60 g (or Resonium A 60 g). Administer furosemide 20 mg IV x 1 • Administer calcium gluconate 100 - 200 mg/kg IV slowly if there is ECG/telemetry evidence of life-threatening arrhythmias. • Recheck potassium, phosphorus, uric acid, calcium and creatinine in 1 hour STAT. If potassium < ULN 1 hour later, repeat potassium phosphorus, uric acid, calcium and creatinine 1, 2, and 4 hours, if no other evidence of tumor lysis. • Potassium ≥ 6.0 mmol/L • Perform STAT ECG and commence telemetry. (6.0 mEg/L) and/or • Nephrology (or other acute dialysis service) assessment symptomatic (eg, muscle with consideration of initiating dialysis. cramps, weakness, Administer Kayexalate 60 g (or Resonium A 60 g). paresthesias, nausea, Administer furosemide 20 ma IV x 1. vomiting, diarrhea) Administer insulin 0.1 U/kg IV + D25 2 mL/kg IV. Administer sodium bicarbonate 1 to 2 mEq/kg IV push. If sodium bicarbonate is used, rasburicase should not be used as this may exacerbate calcium phosphate precipitation. Administer calcium gluconate 100 to 200 mg/kg IV slowly if there is ECG/telemetry evidence of life-threatening arrhythmias. Do not administer in same IV line as sodium bicarbonate. Recheck potassium, phosphorus, uric acid, calcium and creatinine every hour STAT.

Page 1 of 3

Protocol Number: 20200392

Date: 28 April 2022 Page 138 of 149

Table 11-6. Tumor Lysis Syndrome Management Recommendations

| Hyperuricemia | |
|--|--|
| • Uric acid ≥ 8.0 mg/dL (476 μmol/L) | Consider rasburicase (0.2 mg/kg as an intravenous infusion over 30 minutes). |
| | If rasburicase is used, sodium bicarbonate should not be used as this may exacerbate calcium phosphate precipitation. |
| | Recheck potassium, phosphorus, uric acid, calcium and creatinine in 1-hour STAT. |
| • Uric acid ≥ 10 mg/dL (595 μmol/L) | Administer rasburicase (0.2 mg/kg as an intravenous infusion over 30 minutes). |
| OR | When rasburicase is used, sodium bicarbonate should not be used as this may exacerbate calcium phosphate precipitation. |
| • Uric acid ≥ 8.0 mg/dL | Consult nephrology (or other acute dialysis service). |
| (476 μmol/L) with 25% increase and creatinine | Recheck potassium, phosphorus, uric acid, calcium and creatinine in 1-hour STAT. |
| increase ≥ 0.3 mg/dL (≥ 0.027 mmol/L) from pre-dose level | If uric acid < 8.0 mg/dL 1 hour later, repeat potassium, phosphorus, uric acid, calcium and creatinine 2 and 4 hours later, if no other evidence of tumor lysis. |
| Hypocalcemia | |
| • Calcium ≥ 7.0 mg/dL (1.75 mmol/L) | Administer calcium gluconate 50 to 100 mg/kg IV slowly with ECG monitoring. |
| • AND | Telemetry. |
| Patient symptomatic (eg, muscle cramps hypotension, | Recheck potassium phosphorus, uric acid, calcium and creatinine in 1-hour STAT. |
| tetany, cardiac arrhythmias) | If calcium normalized 1 hour later, repeat potassium, phosphorus, uric acid, calcium and creatinine 2 and 4 hours later, if no other evidence of tumor lysis. |
| | Calculate corrected calcium and check ionized calcium if albumin low. |
| Hyperphosphatemia | |
| • Phosphorus ≥ 5.0 mg/dL (1.615 mmol/L) with ≥ 0.5 mg/dL (0.16 mmol/L) | Administer a phosphate binder (eg, aluminum hydroxide, calcium carbonate, sevelamer hydroxide, or lanthanum carbonate). |
| increase | Nephrology (or other acute dialysis service) notification (dialysis required for phosphorus uric ≥ 10 mg/dL). |
| | Recheck potassium, phosphorus, uric acid, calcium and creatinine in 1 hour STAT. |
| | If phosphorus < 5.0 mg/dL 1 hour later, repeat potassium, phosphorus, uric acid, calcium and creatinine 2 and 4 hours later, if no other evidence of tumor lysis. |

Page 2 of 3

Protocol Number: 20200392

Date: 28 April 2022 Page 139 of 149

Table 11-6. Tumor Lysis Syndrome Management Recommendations

| Creatinine | |
|--------------------------------|---|
| • Increase ≥ 25% from baseline | Start or increase rate of IV fluids. Recheck potassium, phosphorus, uric acid, calcium and creatinine in 1 to 2 hours STAT. |

Page 3 of 3

ECG = electrocardiogram; IV = intravenous; ULN = upper limit of normal Reference: Protocol for: Roberts AW, Davids MS, Pagel JM, et al. Targeting BCL2 with venetoclax in relapsed chronic lymphocytic leukemia. *N Engl J Med.* 2016;374:311-322. DOI: 10.1056/NEJMoa1513257

Protocol Number: 20200392

Date: 28 April 2022 Page 140 of 149

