5.1 Inclusion Criteria

Subjects are eligible to be included in the study only if all of the following criteria apply:

- 101 Age \geq 18 years of age.
- Eastern Cooperative Oncology Group (ECOG) performance status of 0 to 2. Refer to Section 11.11.1 for more details.
- For Part 1, patients have R/R MDS post-HMA failure, defined as prior receipt of 4 cycles of HMA therapy (including but not limited to decitabine, azacitidine, investigational HMAs such as SGI-110, and oral HMAs such as ASTX727 and CC-486) with failure to attain a response or progression of disease or relapse at any time after prior response to HMA therapy.

Note:

Protocol Number: 20200392

Date: 28 April 2022 Page 45 of 149

1) Patients with HR-CMML (CMML, CMML-1 or 2 by World Health Organization [WHO]) are eligible.

- 2) Hydroxyurea administration will be allowed on the study to lower the white cell count to $\leq 10\,000/\mu L$ prior to the initiation of therapy.
- 104 For Part 2, patients will be divided into 2 cohorts:
 - a. HMA Failure Cohort: patients with R/R MDS post-HMA failure (defined as prior receipt of 4 cycles of HMA therapy with failure to attain a response or progression of disease or relapse at any time after prior response to HMA therapy) are eligible. Patients who have previously received venetoclax are eligible and will be stratified accordingly in the HMA Failure Cohort.
 - **b.** Newly Diagnosed Cohort: patients with treatment-naïve newly diagnosed HR-MDS (IPSS score ≥ 3.5) are eligible.

Note

- 1) Patients with HR-CMML (CMML-1 or 2 by WHO) are eligible.
- 2) Hydroxyurea administration will be allowed on the study to lower the white cell count to $\leq 10\,000/\mu L$ prior to the initiation of therapy.
- 3) Patients who have previously received venetoclax are eligible and will be stratified accordingly in the HMA Failure Cohort.
- 105 Must be willing and able to undergo bone marrow aspirate at screening.
- Life expectancy of > 3 months, in the opinion of the investigator.
- Hepatic function, as follows: AST, and Alanine Aminotransferase (ALT) < 3 X ULN, total bilirubin < 1.5 X ULN (except subjects with Gilbert's syndrome).
- 108 Cardiac function, as follows; Left Ventricular Ejection Fraction (LVEF) > 50% 2D transthoracic ECHO is the preferred method of evaluation. Multigated Acquisition (MUGA) scan is acceptable if ECHO is not available.

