 - Positive Hepatitis C Virus Antibody (HCVAb): hepatitis C virus RNA by PCR is necessary. Detectable hepatitis C virus RNA suggests chronic hepatitis C. Negative for PCR test can be enrolled in the study.

Prior/Concomitant Therapy

- 211 Treatment with medications known to cause corrected QT Interval (QTc) interval prolongation within 1 week prior to enrollment unless approved by the Amgen Medical Team.
- Anti-tumor therapy: chemotherapy within 14 days (or 5 half-lives, whichever is shorter) of enrollment, antibody therapy, molecular targeted therapy, or investigational agent within 21 days (or 5 half-lives, whichever is shorter) of

Protocol Number: 20200392

Date: 28 April 2022 Page 47 of 149

enrollment. Exceptions: hydroxyurea to control peripheral blood leukemic cell counts is allowed until prior to receiving the first dose of AMG 176.

- 213 Prior systemic radiation therapy must have been completed at least 28 days prior to enrollment. Prior focal radiotherapy completed at least 14 days prior to enrollment.
- Patient has received a live attenuated vaccine within 4 weeks prior to the first dose of study drug. Patients who have received coronavirus disease 2019 (COVID-19) vaccine within **14** days prior to dosing, or plan to receive a COVID-19 vaccine within 28 days postdose; from 29 days postdose through EOS, vaccination for COVID-19 may be deemed acceptable for a subject following discussion and agreement between the sponsor and the investigator.
- Use of any medications (except anti-tumor medications), including herbal medicines (eg, St. John's wort), vitamins, or supplements consumed by the subject within the 30 days prior to enrollment, and continuing use if applicable, that was not reviewed and approved by the PI and the Amgen Medical Monitor prior to enrollment. Written documentation of this review and Amgen acknowledgment is required for subject participation.
- Use of known strong inhibitors of CYP3A4/P-gp within the 14 days or 5 half-lives (whichever is longer) or products containing grapefruit juice, Seville oranges, or St. John's wort within 7 days, prior to enrollment unless reviewed and approved by the principal investigator and the Amgen medical monitor prior to enrollment. Written documentation of this review and Amgen acknowledgment is required for subject participation.

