- Use of known CYP3A4 sensitive substrates with a narrow therapeutic window within 5 half-lives of the drug or its major active metabolite, whichever is longer, following the last dose of the drug prior to receiving the first dose of AMG 176 unless reviewed and approved by the principal investigator and the Amgen medical monitor prior to enrollment. Written documentation of this review and Amgen acknowledgment is required for subject participation. Refer to prescribing information for any concomitant medications.
- 218 Use of known OATP1B1 and/or OATP1B3 or BCRP substrates with a narrow therapeutic window within 5 half-lives of the drug or its major active metabolite, whichever is longer, following the last dose of the drug prior to enrollment unless reviewed and approved by the principal investigator and the Amgen Medical Monitor prior to enrollment. Written documentation of this review and Amgen acknowledgment is required for subject participation. Refer to prescribing information for any concomitant medications.
- 219 Major surgery within 28 days of enrollment.

Prior/Concurrent Clinical Study Experience

Currently receiving treatment in another investigational device or drug study, or less than 30 days since ending treatment on another investigational device or drug study(ies). Other investigational procedures while participating in this study are excluded.

Diagnostic Assessments

Subjects with elevated cardiac troponin above the manufacturer's 99th percentile upper reference limit for ADVIA Centaur XP TnI assay at screening performed by the central laboratory.

Protocol Number: 20200392

Date: 28 April 2022 Page 48 of 149

Subjects with evidence of recent cardiac injury at screening based on Creatine Kinase-Muscle/Brain (CK-MB), N-Terminal Prohormone of Brain Natriuretic Peptide (NT-pro BNP), and Electrocardiogram (ECG) assessments at screening.

Patient has a white blood cell count > 10×10^9 /L. Hydroxyurea or leukapheresis are permitted to meet this criterion.

Other Exclusions

- Female subjects of childbearing potential unwilling to use highly effective methods of contraception (see Section 11.5) during treatment and for an additional 3 months after the last dose of investigational product.
- Female subjects who are breastfeeding or who plan to breastfeed while on study through 3 months after the last dose of investigational product.

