6.7.2 Concomitant Treatment

Throughout the study, investigators may prescribe any concomitant medications or treatments deemed necessary to provide adequate supportive care except for those listed in Section 6.1.7.

Concomitant therapies are to be collected from informed consent through the 30 days (+ 3 days) after the last dose of protocol-required therapies. For concomitant therapies being taken for the disease under study (eg, steroids, chemotherapy on oncology studies), assist in the evaluation of efficacy or safety endpoints, in a specific class, collect therapy name, indication, dose, unit, frequency, start date, and stop date.

Protocol Number: 20200392

Date: 28 April 2022 Page 72 of 149

For all other concomitant therapies, collect therapy name, indication, dose, unit, frequency, route, start date, and stop date.

The investigator must be informed as soon as possible about any medication taken from the time of screening until the end of the clinical phase of the study (final study visit). Any concomitant medication(s), including herbal preparations, taken during the study will be recorded in the electronic Case Report Form (eCRF). The minimum requirement is that drug name, dose, and the dates of administration are to be recorded. Additionally, a complete list of all prior cancer therapies will be recorded in the eCRF.

Subjects should receive full supportive care during the study, including transfusions of blood and blood products, and treatment with antibiotics, anti-emetics, anti-diarrheals, and analgesics, G-CSF and other care as deemed appropriate, and in accordance with their institutional guidelines. Hydroxyurea may be administered according to standard practice prior to the first cycle of AMG 176 treatment for subjects with high WBC (> 15000 cells/uL) and during the first cycle but not on days of AMG 176 administration.

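### The protocol gives different white-cell limits before first dosing (10, 20 and, with azacitidine, 25 x 10^9/L), and its hydroxyurea wording is not aligned across sections

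*Protocol*

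**What the plan says.** **White-cell count before first dosing**

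- Section 5.2 excludes a subject if "Patient has a white blood cell count > 10" x 10^9/L and adds that "Hydroxyurea or leukapheresis are permitted to meet this criterion". It gives no time point for the count.
- Section 5.1, in the notes to criteria 103 and 104: "Hydroxyurea administration will be allowed on the study to lower the white cell count to" 10 000/µL or less, before therapy begins. The synopsis repeats this.
- Section 11.9.2: "Subjects with medium (white blood cell [WBC] 10 to 20) risk for tumor lysis should be initiated on allopurinol" or another uric-acid-lowering treatment before therapy. Above 20, the instruction is to cytoreduce or delay, and to "make sure the WBC to less than 20 prior to starting therapy in protocol". No unit is printed for any of these figures; 10^9/L is implied.
- Section 11.9.3: "All patients should have WBC count less than 25 x" 10^9/L, before azacitidine is started.

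**Hydroxyurea**

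- Section 5.2, as an exception within the anti-tumor therapy washout criterion: "hydroxyurea to control peripheral blood leukemic cell counts is allowed until prior to receiving the first dose of AMG 176".
- Section 6.1.7 lists anti-tumor therapy, including chemotherapy, among treatments not to be given during the study. Hydroxyurea is not named as an exception.
- Section 6.7.2 allows concomitant treatment apart from what Section 6.1.7 lists. It then allows hydroxyurea before the first cycle for a high count ("> 15000 cells/uL) and during the first cycle but not on days of AMG 176 administration").

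**The concern.** These sections bear on the same decision: whether a subject may receive the first dose at the count seen on day 1. Section 6.1.4.1 names an elevated leukocyte count as a risk factor for tumor lysis syndrome, and Section 2.3.2 records a fatal outcome with AMG 176. A site holding a day-1 count above 10 would find a different answer depending on the section it opened, and two sites could handle the same subject differently while each followed the protocol.

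The hydroxyurea wording raises a smaller statistical question. Cycle 1 is the 28-day DLT evaluation period (Section 6.2.1.1). A drug used to lower counts, given in that window under unclear rules, could blur the attribution of a hematologic event to AMG 176.

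**Working it through.** There is no plan figure to reproduce. The check is a comparison of text after conversion to one scale.

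**Unit conversion.** 10 000/µL = 10 x 10^9/L (Section 5.1). 15 000/µL = 15 x 10^9/L (Section 6.7.2).

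**Time points.** AMG 176 is first given on day 1, and azacitidine is given on days 1 to 7 (Section 1.3, dosing footnotes). In the combination parts all the limits therefore meet on the same day. Screening lasts up to 14 days (Section 8.1.1), so the count that qualified a subject can be up to two weeks old. Section 11.9.3 requires hematology within 4 hours before AMG 176, so a fresh count is available on day 1.

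**What each section implies for a day-1 count (x 10^9/L)**

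| Day-1 count | Sections 5.1/5.2 | Section 11.9.2 | Section 11.9.3 (azacitidine only) |
|---|---|---|---|
| 10 or less | within limit | within limit | within limit |
| above 10, below 20 | above limit; hydroxyurea may be used to lower it first | medium-risk group: allopurinol, then start | within limit |
| above 20, below 25 | above limit | cytoreduce or delay | within limit |
| 25 or more | above limit | cytoreduce or delay | above limit |

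The sections agree in the first and last rows and disagree in the middle two. A count of exactly 20 falls inside the 10-to-20 group yet is not below 20, so Section 11.9.2 is also unclear at its own edge.

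**Size by study part**

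- Part 1A (no azacitidine): 10 against 20, ratio 20/10 = 2. The sections disagree for counts above 10 and below 20.
- Parts 1B and 2: 10 against 20 against 25, ratio 25/10 = 2.5. They disagree for counts above 10 and below 25.

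**Hydroxyurea, by period**

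| Period | Section 5.2 | Section 6.1.7 | Section 6.7.2 |
|---|---|---|---|
| Before first AMG 176 dose | allowed | not addressed by name | allowed, described for counts above 15 |
| Cycle 1, not an AMG 176 day | outside the stated end point | barred if hydroxyurea counts as chemotherapy | allowed |
| Cycle 1, AMG 176 day | outside the stated end point | barred if hydroxyurea counts as chemotherapy | not allowed |

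The figure of 15 is also out of line with entry. At a count of 12, Sections 5.1 and 5.2 contemplate hydroxyurea to reach 10, while Section 6.7.2 describes use before cycle 1 only above 15.

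**The case against.** **The limits are nested.** A subject at or below 10 also satisfies 20 and 25, and the entry rule applies to everyone. That is true at entry. It does not settle a count that rises afterwards. The Section 5.1 notes place the target of 10 before initiation of therapy, but they are written as permission to use hydroxyurea, not as a rule to hold the dose. Section 11.9.2 provides for starting at 10 to 20, a group that would be empty if 10 governed at initiation.

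**The tumor lysis safeguards do not depend on the count.** Allopurinol or an equivalent, hospitalization, hydration and electrolyte review are specified for all subjects. This stands and limits the safety consequence. A reader might infer that subjects were left unprotected; the documents do not support that.

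**The hydroxyurea conflict is one of scope.** A reader might infer that the protocol both stops hydroxyurea at the first dose and allows it afterwards. The Section 5.2 sentence sits inside a prior-therapy washout and can fairly be read as governing eligibility only. What remains is that Section 6.1.7 has no named exception while Section 6.7.2, which defers to Section 6.1.7, allows hydroxyurea in cycle 1.

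**DLT and response are already protected.** A reader might infer that cycle-1 hydroxyurea undermines both. Section 6.2.1.1 allows confounded subjects to be declared non-evaluable and replaced. Table 6-2 requires grade 4 neutropenia or thrombocytopenia to last at least 28 days in the absence of active disease. Appendix 12 requires count resolution on at least two analyses over at least 8 weeks, and SAP Appendix E requires responses to last at least 4 weeks. Counts lowered only during cycle 1 would not by themselves establish a response. This objection largely stands, although replacement is at the Medical Monitor's discretion.

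**Conclusion.** The inconsistency is real and lies in current protocol text. Before first dosing the limits differ 2-fold in Part 1A and up to 2.5-fold where azacitidine is given. The larger ratio should not be read as applying to the whole trial. Nor is 15 x 10^9/L a further dosing limit; it describes when hydroxyurea may be used. The hydroxyurea wording is misaligned rather than flatly contradictory, and its effect on DLT assessment is secondary.

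This rests on two assumptions: that the unprinted unit in Section 11.9.2 is 10^9/L, and that counts can rise between the qualifying test and day 1. The documents do not say how often that happens, or how often hydroxyurea would be given in cycle 1, so no number of affected subjects can be stated.

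The SAP reports early termination, no enrolment in Part 2, and analysis mainly by listings, with a responder listing for Part 1A only. The effect on reported results is therefore likely to be small. The point still merits correction because it concerns a pre-dose safety threshold.

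**What to change.** Reconcile Sections 5.1, 5.2, 6.1.7, 6.7.2, 11.9.2 and 11.9.3, with the synopsis notes, so that:

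1. one white-cell limit, with its unit and the time of the qualifying count, applies on day 1, and any difference intended between monotherapy and combination is stated;
2. one on-study hydroxyurea window applies, and Section 6.1.7 refers to it explicitly.

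The choice of limit and window belongs to the clinical team. The cost is amendment wording, or care when this text is reused.

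As the study has closed early, the study report could state which limit was applied on day 1 and list any cycle-1 hydroxyurea beside the DLTs. SAP Section 9.6.10 currently provides no concomitant-medication output. Protocol Section 6.7.2 already requires the data to be collected, so this would cost one listing.
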